Dressing materials are known to influence postoperative surgical wound healing and scar formation. A particular dressing that could promote wound hydration is key to ensure quick epithelialization and decrease excessive scar formation. The current standard of care in wound healing is to promote a moist wound environment by regular changing dressing and hydrate wound when needed. Some new advanced dressing and products have been also suggested with promising results in reducing excessive scar formation such as the use of silicone sheeting, hydrogel wound dressing, etc. However, level-1 evidence studies for effectiveness of such interventions are still lacking. Using advanced dressing enabling effective oxygen delivery to the wound bed could promote tissue hydration, which in turn could accelerate epithelialization and reducing the likelihood of formation of necrotic tissue and excessive scars.

In this study, we hypothesis that using novel dressing allows delivery tissue oxygenation via OxyGeni Oxygen Delivery System will reduce the likelihood of necrotic tissue as well as severe incisional scar post-surgical closure by improving transcutaneous oxygen levels during wound healing process. OxyGeni Oxygen delivery system is a novel wound healing therapy that promises to enhance tissue hydration, which in turn may lead to quick epithelialization essential to reduce the likelihood of formation of necrotic tissue and excessive scars. We will examine the validity of this hypothesis using a pilot randomized controlled trial using a convenient sample of 60 people (30 subjects per arm) with surgical wound closure.

Section D: Purpose and Objectives

We are proposing a clinical study at Baylor College of Medicine, to test the efficacy of the novel OxyGeni Oxygen delivery system for use in caring for patients with surgically closed wounds. We will assess the benefits of this novel therapy on successful closure, vascular parameters and quality of life. The study device OxyGeni is a Class II medical device which has US Food and Drug Administration (FDA) 510(k) clearance, CE-Mark approval and a Health Canada license for the treatment of wounds.

Here are the aims and hypotheses for this study:

Aim1: To assess effectiveness of OxyGeni oxygen delivery system in reducing the likelihood of wound complication postsurgical closure.

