This is a pilot study. We plan to recruit a convenient sample of 60subjects (30 subjects per group), which we anticipate to be sufficient to observe a trend between groups to examine proof of concept of EO2 OxyGeni oxygen to reduce the likelihood of wound complication post-surgical wound closure. Based on our initial prevalence chart review, we anticipate that 20-30% of patients in the control group will have failure in wound closure (e.g. necrosis, tissue necrosis and its volume, infection, surgical revision). We anticipate to reduce the incident of wound complication to less than 5%. Using a chi-square test and assuming an alpha level of 5%, and ratio risk reduction of 25%, we anticipate to have statistical power of 95% using a 30 sample per group.

Based on this pilot study, we will calculate power and will design a clinical trial accordingly.

G2. Data Analysis

Provide a description of your plan for data analysis. State the types of comparisons you plan (e.g. comparison of means, comparison of proportions, regressions, analysis of variance). Which is the PRIMARY comparison/analysis? How will the analyses proposed relate to the primary purposes of your study?

The primary outcome of this study is the percentage of wound complication incidents post surgical interventions. We will use chi-square to estimate whether the number of wound complication incidents is less in the intervention group compared to the control group. The secondary outcomes of this study are: improvement in skin perfusion and reduction in perceived pain, anxiety, and stress. We will use general linear model (GLM) univariate analysis (UNIANOVA) to examine significant difference between groups for the secondary parameters of interest. Results will be adjusted by demographic information (age, gender, BMI) and clinical information (size of initial wound, A1C level, baseline skin perfusion).

Section H: Potential Risks/Discomforts

H1. Potential Risks/Discomforts

Describe and assess any potential risks/discomforts; (physical, psychological, social, legal, or other) and assess the likelihood and seriousness of such risks:

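### The stated 95% power with 30 per group does not follow from the plan's own rates: at 5% on the intervention, two-sided power is about 45–78%

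*Combined protocol and SAP*

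**What the plan says.** All the inputs are in one paragraph of Section G1 (Sample Size).

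- Control rate: "we anticipate that 20-30% of patients in the control group will have failure in wound closure".
- Intervention rate: "We anticipate to reduce the incident of wound complication to less than 5" per cent. No point value is given.
- Test: "Using a chi-square test and assuming an alpha level of 5" per cent, with no statement of one or two sides.
- Effect, power and size: "ratio risk reduction of 25%, we anticipate to have statistical power of 95% using a 30 sample per group".

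The same paragraph calls the study a pilot with a convenience sample, meant to show a trend and to inform the power calculation of a later trial. Section G2 makes the chi-square comparison of complications the primary analysis and words it directionally: it will estimate "whether the number of wound complication incidents is less in the intervention group" compared with control. The background text before Section D says of the device hypothesis: "We will examine the validity of this hypothesis using a pilot randomized controlled trial using a convenient sample of 60 people".

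**The concern.** A power of 95% for 30 against 30 patients, with a binary outcome and a control rate of 20–30%, looks too high. It needs a very large effect, and the paragraph does not say which effect was used. The intervention rate is only bounded. The 25% reduction has no scale, and its wording suggests a relative reduction, which conflicts with the rates beside it.

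This is the only power figure for the primary comparison. A reader who accepts it will take the chance of missing the anticipated effect to be 5% and will read a non-significant chi-square as fairly strong evidence against the device. If the true power is well below 95%, that reading is wrong. The unclear effect scale could also carry over into the later trial that this pilot is meant to inform.

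**Working it through.** **Inputs (Section G1).** n = 30 per group; alpha 0.05; control rate p1 = 20%, 25% or 30%; intervention rate p2 = 5%, the upper bound. Sidedness is not stated, so both were tried.

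**Normal approximation, pooled variance.** With p̄ = (p1 + p2)/2,

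power = Φ{ [ (p1 − p2)√n − z·√(2p̄(1 − p̄)) ] / √(p1(1 − p1) + p2(1 − p2)) }, where z = 1.96 (two-sided) or 1.645 (one-sided).

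For 30% against 5%, two-sided: p̄ = 0.175; (0.25)√30 = 1.369; 1.96·√(2 × 0.175 × 0.825) = 1.053; denominator √(0.21 + 0.0475) = 0.507. Power = Φ(0.316/0.507) = Φ(0.623) = 73.3%.

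**Exact calculation.** All 31 × 31 possible outcome tables were enumerated, and the binomial probabilities of those that the test rejects were summed.

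| Method, p2 = 5% | Control 20% | Control 25% | Control 30% |
|---|---|---|---|
| Two-sided, pooled normal | 41.7% | 58.6% | 73.3% |
| Two-sided, exact uncorrected chi-square | 45.3% | 63.3% | 77.8% |
| Two-sided, Fisher or continuity-corrected | 24.1% | 43.6% | 63.1% |
| One-sided, pooled normal | 54.6% | 70.8% | 83.1% |
| One-sided, exact uncorrected chi-square | 59.3% | 75.9% | 87.4% |

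No cell reaches 95%. By the pooled normal formula, two-sided 95% power against a 5% rate needs 124, 80 and 58 per group.

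**How low must the intervention rate be?** The largest p2 that gives 95% power (exact uncorrected chi-square) is:

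| | Control 20% | Control 25% | Control 30% |
|---|---|---|---|
| Two-sided | none (87.7% at p2 = 0) | 0.25% | 1.4% |
| One-sided | 0.1% | 1.2% | about 2.65% |

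By the two-sided pooled normal formula, 95% is not reached even at p2 = 0 (75%, 85% and 92%). The same holds for two-sided Fisher (57%, 80% and 92%).

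**The 25% as a relative reduction.** Going from 20% to 5% is a reduction of 15/20 = 75%, and from 30% to 5% it is 25/30 = 83%, so a relative 25% contradicts the stated rates. Tested directly (20% to 15%, 25% to 18.75%, 30% to 22.5%), it gives about 7–10% two-sided power with the uncorrected test.

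**The 25% as percentage points.** This reading fits the stated ranges, from 30% against 5% through to 25% against 0%:

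| Control vs intervention | 30 vs 5 | 29 vs 4 | 28 vs 3 | 27 vs 2 | 26 vs 1 | 25 vs 0 |
|---|---|---|---|---|---|---|
| Two-sided exact power | 77.8% | 81.1% | 84.6% | 88.4% | 92.3% | 96.3% |

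Two-sided, the stated figure appears only when the intervention removes essentially every complication.

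**Another possible source.** 30% against 5% with 60 per group gives 95.9% (two-sided, pooled normal). The total may have been entered as the group size, but the documents cannot confirm this.

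**The case against.** The plan says below 5%, not 5%. Power at exactly 5% is therefore a floor for each control rate, and 95% is compatible with the text: 25% against 0% lies at the edge of the stated ranges and gives 96.3% with the stated test. The wording in G2 is directional. If a one-sided test was meant, a 30% control rate needs only about 2.65% on the intervention, roughly half the ceiling and hardly near zero. Percentage points are the only coherent reading of the 25%, so the 7–10% power describes a scenario the plan probably did not intend. Finally, the study is labelled a pilot and exploratory, its size is one of convenience, and the hypothesis in the background concerns necrosis and scarring rather than the full complication composite.

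Much of this stands. The figures at 5% are lower bounds, the near-zero requirement is strictly a two-sided result, and the background sentence lends only limited weight. The pilot label is a good reason to leave the sample size alone. But a power figure needs a point assumption and a sidedness, and no other part of the documents supplies them. Two-sided, a control rate of 20% never gives 95%. One-sided, the rates needed are not stated either. Calling the study a pilot does not make a numerical claim correct.

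**Conclusion.** The concern holds. At the plan's 5% bound, two-sided power with 30 per group is 45–78% (exact chi-square) or 42–73% (pooled normal) across control rates of 20–30%, and no method or sidedness tried exceeds 87.4%. The two-sided chance of missing the effect there is 22–55% (exact) or 27–58% (normal), not 5%. The 95% depends on assumptions the plan does not make: an intervention rate at or close to zero with a two-sided test, or at most about 2.65% with a one-sided test at the top of the control range.

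These results assume 30 analysed patients in each group, no dropout and the uncorrected chi-square test. A continuity correction or Fisher's test lowers power further. The conclusion concerns the stated figure, not the choice of 60 patients.

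**What to change.** Keep the sample of 60. In Section G1, state the sidedness, the assumed intervention rate and the scale of the reduction, and replace the 95% with, for example:

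> With 30 per group and a two-sided chi-square test at 5%, power is about 45%, 63% and 78% (exact; 42%, 59% and 73% by normal approximation) for control rates of 20%, 25% and 30% if the intervention rate is 5%, and higher if it is lower.

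If the 95% rested on a lower intervention rate or a one-sided test, state that rate and that test with the matching power, and make G2 agree.

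Delete the 25% reduction or restate it as an absolute reduction. At an intervention rate of 5% this is 15–25 percentage points; at lower rates it is larger.

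In Section G2, add the risk difference with its 95% confidence interval. As a planning guide, 1.96·√(p1(1 − p1)/30 + 0.05 × 0.95/30) gives half-widths of 16.3, 17.3 and 18.2 points for control rates of 20%, 25% and 30%. With only 30 × 0.05 = 1.5 events expected on the intervention, this simple formula is rough, so the plan should name an interval method suited to small counts, such as a score-based one.

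The cost is protocol wording and one confidence interval, with no extra patients or visits. The only drawback is a less favourable stated power.

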H1: OxyGeni oxygen delivery system will reduce the likelihood of surgical wound complication including tissue necrosis and its volume, infection, surgical revision, and amputation compare to standard of care dressing.

Aim2: To assess changes in skin perfusion in patients treated with OxyGeni oxygen delivery system.

H2: OxyGeni oxygen delivery system will improve perfusion in >50% of the patients as compared to baseline (measurements at baseline, 2 weeks, and 4 weeks).

Aim3: To evaluate changes in quality of life, anxiety during dressing change, and psychosocial parameters in patients with a surgical wound treated by OxyGeni oxygen delivery system

H3: Oxygen delivery will improve subject quality of life, reduce anxiety, and reduce perceived pain and physiological stress response during dressing change compared to the control group.

Aim4: To assess acceptability, user-friendliness, and Perception of benefit.

H4: OxyGeni oxygen delivery system will be considered to be practical to use, easy to use, and is perceived to be beneficial from both practitioner and subject as assessed by user friendliness questionnaire adapted for the purpose of this study (assessment at the conclusion of the study). This questionnaire is attached to the protocol.

H5. OxyGeni oxygen delivery system therapy will improve scar cosmetic appearance as assessed practitioner using the Scar Cosmesis Assessment and Rating (SCAR) Scale.

This is an exploratory study and our parameters of interest are: ¿ Complete wound healing post surgical intervention. ¿ % of wound complication post-surgical wound closure ¿ Perfusion improvement at 2 weeks, 4 weeks and 6 months compared to baseline and compared to the control group. ¿ Differences in pain, stress, anxiety, and quality of life compared to the control group ¿ Device acceptability and perception of benefit

Section E: Protocol Risks/Subjects

E1. Risk Category

Category 2: Research involving greater than minimal risk, but presenting the prospect of direct benefit to the individual subjects.

E2. Subjects

Gender:

Both

Age:

Adult (18-64 yrs), Geriatric (65+ yrs)

Ethnicity:

All Ethnicities

Primary Language:

English, Spanish

Groups to be recruited will include:

Patients

Which if any of the following vulnerable populations will be recruited as subjects?

Vulnerable populations require special protections. How will you obtain informed consent, protect subject confidentiality, and prevent undue coercion?

E3. Pregnant woman/fetus

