Will pregnant women and/or fetuses (as described in 45 CFR 46 Subpart B) be enrolled in the research? No

E4. Neonates

Will neonates of uncertain viability or nonviable neonates (as described in 45 CFR 46 Subpart B) be enrolled in the research?

E5. Children

Will children be enrolled in the research?

Section F: Design/Procedure

F1. Design

Select one category that most adequately describes your research:

c) Pilot

Discuss the research design including but not limited to such issues as: probability of group assignment, potential for subject to be randomized to placebo group, use of control subjects, etc.

This study will be a 4 weeks prospective (or up to wound healing or surgical revision, whichever came first), experimental study with N=60 consecutive patients, who are undergoing surgical closure.

Subjects will be randomized to either control or intervention group. The intervention group will receive the OxyGeni device and place the oxygen delivery within SOC dressing. The control group will receive standard of care wound dressing.

All patients will have baseline assessment including visual, dermal, neuropathy (Vibration Perception Threshold) and vascular assessment (ABI and Skin Perfusion Pressure). Then, the status of wound closure and presence of wound complication will be monitored every week. Each subjects will need up to 5 visits including baseline assessment, and weekly assessment up to 4 weeks or full wound healing or surgical revision, whichever came first, and an additional follow-up visit at a minimum 6 months after the surgery. At each visit, patients will be provided standard of care treatment including physical assessment, debridement and offloading. Table 1 in attachments' section summarizes the key measurement at each study visit.

Please note that no screening activities will take place prior to the patient signing a consent form.

Inclusion Criteria:

18-85 years of age. Ability to provide informed consent. Presence of a wound due to surgical intervention and closure. Subject or responsible caregiver is willing and able to maintain the required offloading (as applicable for the location of the wound) and applicable dressing changes

Exclusion Criteria:

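### Ankle-based perfusion measures cannot describe a non-leg incision, and the promised 6-month perfusion comparison has no SPP or ABI value

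*Combined protocol and SAP*

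**What the plan says.** G2 (Data Analysis) gives the outcome in these words: "The secondary outcomes of this study are: improvement in skin perfusion and reduction in perceived pain, anxiety, and stress". The arms are compared with a univariate general linear model, adjusted for demographic data and for "clinical information (size of initial wound, A1C level, baseline skin perfusion").

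In Section D, H2 expects that the device "will improve perfusion in >50% of the patients as compared to baseline (measurements at baseline, 2 weeks, and 4 weeks"). The parameters of interest in the same section go further: "Perfusion improvement at 2 weeks, 4 weeks and 6 months compared to baseline and compared to the control group".

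F2 (Vascular Assessment) describes SPP with cuffs around the ankles and ABI from ankle and arm, both at baseline and visits 2 and 4. It also plans tissue oxygen saturation images at each visit, with either the Kent or the HyperView camera, and does not state the body site imaged.

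F1 sets the wound criterion as "Presence of a wound due to surgical intervention and closure", with no limit on location. For the six-month follow-up, F2 (Procedure) asks for a photo of the neck from remote patients. For in-person patients it asks for neck images plus Kent camera images to judge scarring and perfusion.

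**The concern.** The treatment is local: oxygen is delivered under the dressing, and Section I speaks of vascular conditions at the wound bed. A perfusion outcome that tests this has to be read at or near the treated tissue. An ankle pressure may do so for a leg or foot wound. It cannot do so for a neck wound, which the eligibility criteria allow and the six-month procedure expects. Each such patient adds a value to the comparison that the treatment has no local route to change.

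The second issue is the 6-month item. It is stated as a comparison with baseline and with control, but the measure that best fits the outcome is not taken then. Whatever is reported at six months will come from a different measure and from patients who chose to return.

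G1 says that the later trial will be designed from this pilot, so an uninterpretable perfusion signal could carry forward.

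**Working it through.** The documents give no effect size, SD or power for perfusion; the power figure in G1 concerns wound complications only. There is no figure to reproduce, so most of this check sets the sections side by side.

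**1. Which measure is meant.**
- G2 speaks of skin perfusion. F2 names skin perfusion pressure, in mmHg, as the measure of the micro-circulation.
- F1 describes the baseline "vascular assessment (ABI and Skin Perfusion Pressure").
- H2's time points are baseline, 2 weeks and 4 weeks. SPP and ABI are taken at baseline, visit 2 (two weeks) and visit 4 (four weeks), an exact match. Saturation images are taken at every visit, which is not the H2 schedule.

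SPP at weeks 2 and 4 is therefore the likeliest reading. Still open are which week is the main one and what counts as improvement.

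**2. What that openness costs.** On the SPP reading there are two candidate between-group tests. Assume each is run at a two-sided 5% level with no true effect. The chance of at least one nominal difference is:
- perfectly correlated tests: 5%;
- independent tests: 1 − 0.95² = 0.0975, or 9.75%.

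For H2, suppose any rise counts and each of 30 treated patients is equally likely to rise or fall. More than 50% means at least 16 of 30, and P(X ≥ 16) for a binomial(30, 0.5) is 0.428. Without a threshold, H2 could be met by chance in about 43% of such trials.

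**3. Site of measurement against site of wound.**

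| Item | Location | Where stated |
|---|---|---|
| SPP | ankle cuffs | F2, Skin Perfusion Pressure |
| ABI | ankle and arm | F2, Ankle-Brachial Index |
| Saturation image | not stated | F2, Vascular Assessment |
| Eligible wound | any surgically closed wound | F1, Inclusion Criteria |
| Six-month images | neck named | F2, Procedure |

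That an ankle reading says nothing about a neck incision is an anatomical inference, but a safe one. With a purely local effect, these patients pull the between-group difference towards zero and add variance. The share of such patients is not given, so the amount cannot be computed.

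**4. What exists at each time point.**

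| Measure | Baseline | Week 2 | Week 4 | 6 months |
|---|---|---|---|---|
| SPP | yes | yes | yes | no |
| ABI | yes | yes | yes | no |
| Saturation image | Kent or HyperView | Kent or HyperView | Kent or HyperView | Kent, in person only |

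SPP is planned at 3 of 6 visits (baseline and visits 1 to 5) and not at Visit 5. The 6-month comparison therefore needs a patient who agrees to the optional visit (J2 requires re-consent), attends in person, and had a Kent rather than a HyperView image at baseline. The Visit 5 list in F2 names scar scales and a picture of the scar, with no perfusion measure.

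**5. What a reduced subset could detect.** For 80% power at a two-sided 5% level, unadjusted, the detectable difference in SD units is (1.960 + 0.842) × √(2/n) for n per arm:
- n = 30: 0.72
- n = 15 (assumed attendance): 1.02
- n = 10 (assumed attendance): 1.25

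These show precision only. They do not address bias from self-selection.

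**The case against.** The strongest defence is that the plan is coherent on a fair reading. SPP is the evident measure, and F2 explains it as a test of small vessels in the feet and of blood supply to wounds. The population looks mainly lower-limb: H1 runs the device tube along the legs, vibration threshold is tested on the foot, a podiatric physician applies the WIfI classification, and Charcot arthropathy and bilateral leg amputation are exclusions. The Wound Assessment in F2 already allows a Kent camera to photograph the wound at every visit. The visit lists are shorthand, since Visits 1 and 3 also omit vascular assessment although saturation images are due at every visit. F1 adds that "Table 1 in attachments' section summarizes the key measurement at each study visit"; that attachment was not available and may settle the schedule. Finally, this is a pilot that calls itself exploratory.

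Much of this stands. A reader might infer that the perfusion outcome is wholly undefined, so that any instrument at any visit could be picked once the data are in, with a correspondingly large false-positive risk. The documents do not support that: wording, baseline assessment and schedule converge on SPP, which leaves two candidate tests. A reader might also infer that no perfusion data exist at six months. That too goes too far, because Kent images are planned for in-person visits.

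The defence does not remove the site problem. The more firmly the outcome is ankle SPP, the less it can say about a non-leg wound. The Kent camera is only one of three options in the Wound Assessment, where the stated purpose is wound size and inflammation. No reading of the schedule in F2 supplies an SPP or ABI value at six months.

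**Conclusion.** The point holds and is minor. If the plan is followed as written, any non-leg wound contributes an SPP or ABI value that cannot show perfusion at the treated incision. The 6-month perfusion comparison would rest on a different measure in a self-selected subset.

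No dilution is quantified, because the documents do not give the share of non-leg wounds and it may be small. The choice between weeks 2 and 4 carries a false-positive chance of 5% to 9.75%, assuming two tests at 5% each; in an exploratory pilot this has modest weight. The conclusion rests on SPP being the intended measure and on a local treatment effect. Table 1 could change the scheduling part. The primary outcome, wound complications, is unaffected.

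**What to change.** 1. In G2, analyse SPP and ABI as perfusion outcomes in lower-extremity wounds only. For pain, anxiety and stress, keep all randomized patients, and do not drop non-leg patients because of the baseline SPP covariate.
2. In F2 (Vascular Assessment), state that the planned Kent or HyperView image is taken at the incision, with the same camera throughout for a given patient. Analyse it for all wound sites with its own baseline as covariate. Note that under continuous local oxygen it may partly reflect delivered oxygen rather than perfusion.
3. In Section D, label the 6-month perfusion comparison descriptive and limit it to patients with both a baseline and an in-person 6-month Kent image, or delete it. Reconcile Section D, the F2 procedure text, the Vascular Assessment, the Visit 5 list and Table 1.
4. In the same edit, name week 2 or week 4 as the main time point and define improvement for H2. The choice should allow for visits that end early, since F1 plans "weekly assessment up to 4 weeks or full wound healing or surgical revision, whichever came first", so some week-4 values may not exist.

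The cost is wording plus one procedural line, with no new visit or device. There are two downsides. The SPP and ABI analysis will have fewer patients, and even on the leg an ankle-cuff value describes the limb rather than a particular toe or foot incision. Saturation is also a different construct from perfusion, so the two results must be reported as such.

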Charcot Arthropathy Bilateral AK/BK amputation Active Drug/alcohol abuse (or history of drug/alcohol abuse in last 1 month) Dementia or impaired cognitive function Subjects with osteomyelitis or extreme gangrene. Excessive lymphedema Presence of active infection Subject has a history of or any intercurrent illnesses or conditions that would compromise the safety of the subject according to judgement of a qualified wound specialist.

F2. Procedure

Please note that subjects will be consented before performing any study related measurements. This study will not bring any direct costs to the subject. The subject's medical insurance will be billed for all standard of care procedures.

Subjects who are randomized in the intervention group will receive the OxyGeni therapy into their SOC dressing. Those subjects allocated to the control group will only receive Standard of Care treatment. We will be reviewing the billing records for our patients to explore costs of both groups.

We may visit the patient's home for an appointment that doesn't require the physician present or to fix any issues with the device.

There will be a follow up phone call up to three months after the last visit. Additionally, there may be an optional six month follow-up that can be conducted remotely (via a video or phone call) or in-person. During the virtual six month follow-up the patient will be asked to answer questionnaires electronically via REDCAP. This will also involve uploading a photo of the neck area to allow for virtual assessment of scarring/wound healing. Finally, the subject will be asked to upload a video of them performing 20 seconds of elbow flexion-extension to allow for virtual frailty assessment. Should the subject be available for an in-person visit, questionnaires will be conducted in clinic. Upper-extremity frailty test will also be conducted in the clinic per description listed below. Digital images of the neck area and images using the Kent camera will be taken to assess scarring and tissue perfusion.

Study Tasks:

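### The planned pain model adjusts for baseline skin perfusion but not for baseline pain, which is already collected: an avoidable loss of precision, not a bias

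*Combined protocol and SAP*

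**What the plan says.** Section G2 names the secondary outcomes: "The secondary outcomes of this study are: improvement in skin perfusion and reduction in perceived pain, anxiety, and stress". It assigns them one type of model: "We will use general linear model (GLM) univariate analysis (UNIANOVA) to examine significant difference between groups for the secondary parameters of interest". It then gives one set of covariates: "Results will be adjusted by demographic information (age, gender, BMI) and clinical information (size of initial wound, A1C level, baseline skin perfusion". The only outcome whose own starting value is in that set is skin perfusion.

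In Section F2, the pain intensity item says that pain is measured at every visit. The visit lists show it at the screening/baseline visit and at visits 1 to 4. The heart rate item schedules the wearable sensor at all visits.

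Hypothesis H3 in Section D expects the device to "reduce perceived pain and physiological stress response during dressing change compared to the control group". No section adds baseline pain to the covariates. None says whether the pain response is the follow-up score or the change from baseline.

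**The concern.** A patient's pain before treatment is usually among the better predictors of that patient's pain afterwards. Here the model would remove variation linked to baseline perfusion and A1C, and leave in the variation linked to baseline pain. G2 already accepts the principle by listing baseline perfusion, so the gap looks like an oversight from using one list for all outcomes.

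Two things are at stake:

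- **Precision.** The interval for the pain difference may be wider than the collected data require.
- **Chance imbalance.** With 30 patients per arm, the difference in mean baseline pain between arms has a standard deviation of √(4/60) = 0.258 SD by chance alone. If the follow-up score is the response, a baseline difference d shifts that trial's estimate by about r × d (ignoring the listed covariates). At r = 0.5 and d = 0.258 the shift is about 0.13 SD. Over repeated trials these shifts average to zero. They are part of the standard error, not an additional error.

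**Working it through.** The plan gives no power or precision figure for any secondary outcome, so there is no figure of its own to reproduce. The check compares the interval width with and without the own baseline.

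**Inputs from the documents.** N = 60, 30 per group (G1). Six planned covariates: age, gender, BMI, wound size, A1C, baseline skin perfusion (G2).

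**Assumptions.** Outcome SD = 1. The six covariates are unrelated to the outcome and to baseline pain. There is one follow-up value per patient and no missing data. The baseline-to-follow-up correlation r is shown over a range because the documents give none.

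**Formula.** Half-width = t(0.975; N − 2 − k) × √[(4/N) × v × (N − 3)/(N − k − 3)]. Here k is the number of covariates and v the residual variance:

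- follow-up score, no own baseline: k = 6, v = 1
- change score, no own baseline: k = 6, v = 2(1 − r)
- own baseline in the model, either response: k = 7, v = 1 − r²

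**Constants.** For k = 6: t(52 df) = 2.0066 and 57/51 = 1.1176, so the half-width is 2.0066 × √(0.06667 × 1.1176) × √v = 0.548 × √v. For k = 7: t(51 df) = 2.0076 and 57/50 = 1.14, so it is 0.553 × √v.

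**Results (95% half-width, in SD).**

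| r | Follow-up, as planned | Change, as planned | With own baseline | Narrower than follow-up | Narrower than change |
|---|---|---|---|---|---|
| 0 | 0.548 | 0.775 | 0.553 | −1% (wider) | 29% |
| 0.3 | 0.548 | 0.648 | 0.528 | 4% | 19% |
| 0.5 | 0.548 | 0.548 | 0.479 | 12.5% | 12.5% |
| 0.7 | 0.548 | 0.424 | 0.395 | 28% | 7% |

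For the follow-up score, adding the baseline pays once r exceeds 0.14. For the change score it pays at every r below 0.96.

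**Sensitivity to decaying correlation.** Suppose the correlation falls with each week as r to the power of the lag.

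- Weekly correlation 0.7: the correlation of baseline with visit 4 is 0.7⁴ = 0.24. The half-width for the visit 4 score is 0.553 × √(1 − 0.24²) = 0.537, about 2% narrower than planned.
- Weekly correlation 0.5: the visit 4 correlation is 0.5⁴ = 0.0625, below break-even. The half-width is 0.552, just under 1% wider.
- Average of visits 1 to 4 as the response: the gains are 0.4%, 4.5% and 15% at weekly correlations 0.3, 0.5 and 0.7.

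The upper rows of the gain are therefore not guaranteed. The worst loss for a follow-up response is about 1%.

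**Fewer patients.** Visits run as "weekly assessment up to 4 weeks or full wound healing or surgical revision, whichever came first", so late visits may have fewer patients. At an assumed N = 48 and r = 0.5, the half-width is 0.627 without own baseline and 0.550 with it, still 12% narrower. Losing patients widens both intervals and leaves the relative gain almost unchanged.

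**The case against.** The strongest case against is that this is a self-described exploratory pilot, randomisation protects the comparison, and the primary analysis is unaffected. All of that stands. The sentence "Based on this pilot study, we will calculate power and will design a clinical trial accordingly" closes a sample-size paragraph that deals only with wound complications, so it adds little weight to the precision of a secondary outcome. The gain also rests on an r that nobody has stated. It would be smaller if the listed covariates already explain part of baseline pain. These points limit the priority of the change. They do not argue for leaving out a covariate that is already collected.

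Some stronger readings are tempting and should be resisted:

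- **Heart rate as a second proven omission.** G2 names stress, not heart rate. The link is inferred from H3 and the wearable sensor. Section F1 also refers to a table of key measurements in an attachment that is not in the reviewed text, so it cannot be said that the stress measure is undefined everywhere.
- **A dressing-change baseline is certainly available.** The baseline visit includes a dressing change and device education, and Section F2 describes placing the oxygen cannula while the dressing is applied. The documents do not say whether the readings come before allocation or before the device. A reading taken afterwards is not a proper baseline.
- **Early end of visits biases the pain comparison, so a repeated-measures model is required.** Nothing in the documents gives the rate or pattern of stopping by arm. That is a separate missing-data question and does not follow from the omitted covariate.

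**Conclusion.** The point holds for pain. It is a named secondary outcome with a scheduled baseline reading, and its model omits that reading while including the baseline of another outcome. The consequence is lost precision and uncorrected chance imbalance.

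Under the stated assumptions, at r between 0.3 and 0.7 the interval would be 4% to 28% narrower if the response is the follow-up score. If it is the change from baseline, it would be 19% to 7% narrower. With a follow-up score the gain can shrink to nothing, or to a loss of about 1%, if the correlation is very low or fades over the weeks.

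A reader might infer that the pain result would be biased or that the trial's main conclusion is at risk. The documents support neither, because allocation is randomised and the primary test is an unadjusted chi-square. For stress and anxiety the point is conditional: the supplied text links stress to heart rate only by inference and names no anxiety instrument. It is worth correcting because it is nearly free, but it is not critical.

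**What to change.** Add one sentence to G2:

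> Each secondary model also includes the baseline-visit value of the same measure, recorded before the device is started, whether the response is the follow-up value or the change from baseline.

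This applies to pain at once. It applies to the stress measure (possibly heart rate, which is collected at all visits) and to anxiety wherever a pre-device baseline of the same measure exists. Skin perfusion gains nothing new, since its baseline is already listed. The sentence should be added before outcome data are analysed, so that the covariates are not chosen with results in view.

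The cost is a wording change and one degree of freedom per model (52 to 51 residual degrees of freedom with 60 patients). Staff must take the baseline reading before the device is applied. No patients, visits or measurements are added.
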